5.6 Subject Withdrawal/Discontinuation Criteria

Subjects may withdraw consent at any time for any reason or be dropped from the trial at the discretion of the investigator should any untoward effect occur. In addition, a subject may be withdrawn by the investigator or Sponsor if enrollment into the trial is inappropriate, the trial plan is violated, or for administrative and/or other safety reasons. Specific details regarding discontinuation or withdrawal are provided in Section 7.1.4 – Other Procedures.

A subject must be discontinued from the trial for any of the following reasons:

- The subject or legal representative (such as a parent or legal guardian) withdraws consent.
- Confirmed radiographic disease progression
- Dose interruption that exceeds 21 days
- Unacceptable adverse experiences
- Any Grade 4 or greater AE
- Severe (Grade 3) or life-threatening (Grade 4) immune-mediated complication
- Intercurrent illness that prevents further administration of treatment
- Investigator's decision to withdraw the subject
- The subject has a confirmed positive serum pregnancy test
- Noncompliance with trial treatment or procedure requirements
- The subject is lost to follow-up
- Death
- Administrative reasons
- Discontinuation of pembrolizumab treatment may be considered for subjects who have attained a confirmed CR and have been treated for at least 8 cycles (at least 24 weeks) of pembrolizumab and have received at least 2 cycles of pembrolizumab beyond the date when the initial CR was declared. These subjects may be eligible for second course treatment as described in Section 5.2.3.
- Completion of 24 months (35 cycles) of pembrolizumab

NOTE: Subjects who stop pembrolizumab after completion of 24 months (35 cycles) may be eligible for retreatment if they progress after stopping pembrolizumab provided they meet the requirements detailed in Section 5.2.3. Subjects may be retreated in the Second Course Phase (Retreatment) for up to an additional 12 months (17 cycles [calculated starting with the first dose]).

The End of Treatment and Follow-up visit procedures are listed in Section 7.1.5 (Visit Requirements). At the end of treatment (EOT), each subject will be followed for 30 days for AE monitoring (SAEs will be collected for 90 days after EOT as described in Section 7.2.3.1). Subjects who discontinue for reasons other than PD will have post-treatment follow-up for disease status until disease progression, initiating a non-study cancer treatment, withdrawing consent, or becoming lost to follow-up. After documented disease progression each subject will be followed by telephone for OS until death, withdrawal of consent, or the end of the study, whichever occurs first.

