5.2 Trial Treatments

The treatments to be used in this trial is outlined below in Table 2

Table 2 Trial Treatments

Drug	Dose/Potency	Dose Frequency	Route of Administration	Regimen/Treatment Period	Use
ADV/HSV-tk	5 x 10 ¹¹ vp in 2-mL volume	Once	Intratumorally	Day 0	Experimental
Valacyclovir	2 g	t.i.d. for 14 days	Orally	Day 1 - Day 15	Experimental
SBRT*	30 Gy	6 Gy X 5 fractions over 14 days	-	Day 2 - Day 16	Experimental

Drug	Dose/Potency	Dose Frequency	Route of Administration	Regimen/Treatment Period	Use
Pembrolizumab**	200 mg	Q3W	IV infusion	Day 1 of each 3-week cycle	Experimental

vp = viral particles; t.i.d. = three times daily; Q3W = every 3 weeks; IV = intravenous.

*Primary breast tumors will be treated with three-dimensional RT (short course of 5–8 fractions).

**Pembrolizumab will continue until disease progression, unacceptable toxicity, or up to 24 months (35 cycles) in subjects without disease progression. All subjects who stop pembrolizumab treatment with complete response may be eligible for up to an additional 12 months (17 cycles) of pembrolizumab treatment if they progress after stopping pembrolizumab from the initial treatment phase. The subject must meet the conditions outlined in Section 5.2.3.

ADV/HSV-tk

The tumor will be identified by positron emission tomography (PET)/CT by the radiation oncologist. ADV/HSV-tk will be administered intratumorally as a single injection using a 21-gauge needle. For nodal, lung, and liver lesions, ADV/HSV-tk will be administered after fiducial placement for SBRT. For primary lung tumors, ADV/HSV-tk will be administered under endobronchial ultrasound (EBUS) guidance. In cases where the tumor cannot be accessed by EBUS, a CT-guided injection will be performed. For primary breast tumors, ADV/HSV-tk will be administered under ultrasound guidance. For liver and lung metastatic lesions, ultrasound or CT-guided injection of ADV/HSV-tk will be performed. EBUS will be performed with the patient under sedation. Patients will be monitored until the sedation has worn off. For CT-guided injections, local anesthesia will be used and patients will be monitored for several hours after the procedure.

SBRT

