tumors will be treated with a short course (5-8 fractions) of three-dimensional RT. SBRT and three-dimensional RT will be administered over 2 weeks from Day 2 to Day 16 of the study. Pembrolizumab at a dose of 200 mg will be intravenously infused over 30 min Q3W (\pm 1 day) starting on Day 17 (\pm 1 day) of the study and continuing until disease progression, unacceptable toxicity, or up to 24 months (35 cycles) in subjects without disease progression. All subjects who stop pembrolizumab treatment with complete response may be eligible for up to an additional 12 months (17 cycles) of pembrolizumab treatment if they progress after stopping pembrolizumab from the initial treatment phase. The subject must meet the conditions outlined in Section 5.2.3.

m. AEs and SAEs will be captured from the time of informed consent signing up to 30 days after the final dose of pembrolizumab. Study treatment-related SAEs and any study patient death occurring beyond 30 days after the last dose of pembrolizumab should also be reported.

*Patients will be treated until disease progression, unacceptable toxicity, or up to 24 months in subjects without disease progression.

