- Overall irPD: $\geq 20\%$ increase in the sum of the longest diameters of target and new measurable lesions (compared to nadir), confirmed by repeat, consecutive observations at least 4 weeks (normally it should be done at 6 weeks) from the date first documented.

Documentation of irPD (based on the modified irRC) does not mandate discontinuation of the study treatment even after irPD is confirmed with CT scan 8 weeks after the initial observation of irPD.

RECIST 1.1 are defined as follows:

Target Lesions (Main Tumor)

- **CR:** Disappearance of all target lesions. Any pathological lymph nodes (whether target or non-target) must have reduction in short axis to < 10 mm.
- **PR:** At least a 30% decrease in the sum of the diameters of target lesions, using the baseline sum diameters as the reference.
- **PD:** At least a 20% increase in the sum of the diameters of target lesions, using the smallest sum on study (includes the baseline sum) as the reference. In addition to the relative 20% increase, the sum must also demonstrate an absolute increase of at least 5 mm. (Note: the appearance of one or more new lesions is also considered progression)
- **SD:** Neither sufficient shrinkage to qualify for PR nor sufficient increase to qualify for PD, using the smallest sum diameters while on study as the reference.

Non-Target Lesions

- **CR:** Disappearance of all non-target lesions and normalization of tumor marker levels. All lymph nodes must be non-pathological in size (< 10 mm short axis).
Note: If tumor markers are initially above the upper normal limit, they must normalize for a patient to be considered in complete clinical response.
- **Non-CR/Non-PD:** Persistence of one or more non-target lesion(s) and/or maintenance of tumor marker levels above the normal limits.
- **PD:** Appearance of one or more new lesions and/or *unequivocal progression* of existing non-target lesions. *Unequivocal progression* should not normally trump target lesion status. It must be representative of overall disease status change, not a single lesion increase.
- Although a clear progression of “non-target” lesions only is exceptional, the opinion of the treating physician should prevail in such circumstances, and the progression status should be confirmed at a later time by the review panel (or investigator).

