7.1.5.1.3 Survival Follow-up

Once a subject experiences confirmed disease progression or starts a new anticancer therapy, the subject moves into the Survival Follow-up Phase and should be contacted by telephone every 12 weeks to assess for survival status until death, withdrawal of consent, or the end of the study, whichever occurs first.

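### Section 5.6 requires discontinuation at confirmed radiographic progression, Section 7.1.2.7 lets treatment go on after confirmed irPD, and nothing says which criterion governs

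*Combined protocol and SAP*

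**What the plan says.** Section 5.6 states that "A subject must be discontinued from the trial for any of the following reasons", and the list that follows includes "Confirmed radiographic disease progression". No response criterion is attached to that entry.

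Section 7.1.2.7 says of irPD, once documented under modified irRC, that it "does not mandate discontinuation of the study treatment even after irPD is confirmed with CT scan 8 weeks after the initial observation of irPD".

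Other sections that depend on progression are worded differently again:

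- **Treatment duration.** The Table 2 footnote in Section 5.2 reads "Pembrolizumab will continue until disease progression, unacceptable toxicity, or up to 24 months (35 cycles) in subjects without disease progression". Section 1.0 and note l of the flow chart in Section 6.1 say the same. None mentions confirmation or a criterion.
- **Follow-up.** The end of Section 5.6 starts telephone contact for survival once progression is documented. Section 7.1.5.1.3 says "Once a subject experiences confirmed disease progression or starts a new anticancer therapy, the subject moves into the Survival Follow-up Phase".
- **Prohibited therapies.** Section 5.3.2 keeps its restrictions in force until progression is documented under both modified irRC and RECIST 1.1.
- **Confirmation interval for irPD.** Section 7.1.2.7 gives 8 weeks in its general description and again in the sentence quoted above, but its definition of irPD gives at least 4 weeks and normally 6. Appendix 12.3 gives at least 4 weeks.

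**The concern.** One section makes stopping mandatory at confirmed progression. Another says that confirmed progression under the immune criteria carries no such obligation. No text ranks the two or says which criterion decides treatment, so two investigators with the same scans could act differently and each cite the protocol.

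Modified irRC results are to be documented alongside RECIST 1.1 (Sections 3.1 and 3.2), because Section 7.1.2.7 expects benefit from immunotherapy to appear late in some patients. Those results, the number of doses given after progression, and the adverse events collected in a window that runs from the last dose would then mix patients handled under different rules. The cohorts are small (28 and 29) and treatment is open label.

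**Working it through.** The plan states no figure on this point, so there is none to reproduce. The check compares the texts and then counts doses and scan dates.

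**1. Does Section 5.6 mean RECIST 1.1 and Section 7.1.2.7 mean modified irRC?** Section 5.6 does not say so, although Section 5.2.3 does name RECIST 1.1 when it defines progression for retreatment. Section 7.1.2.7 presents confirmation of progression as something modified irRC requires in contrast to RECIST 1.1. The only confirmation it mentions under RECIST 1.1 concerns progression in non-target lesions alone. The word confirmed in Section 5.6 therefore points towards modified irRC or is undefined.

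**2. Would that split remove the conflict?** The definitions are those in Section 7.1.2.7, and the same target lesions and diameters are assumed under both criteria.

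- irPD: a rise of at least 20% from nadir in target plus new measurable lesions.
- RECIST 1.1 PD: a rise of at least 20% from the smallest target sum and of at least 5 mm, or any new lesion.
- With a new lesion, RECIST 1.1 PD already applies.
- With none, both sums are the target sum. For nadir sum N, the rise is at least 0.20 × N. It can be below 5 mm only if 0.20 × N < 5, that is N < 5 / 0.20 = 25 mm.

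Outside that corner, a confirmed irPD is also RECIST 1.1 PD. A patient continued under Section 7.1.2.7 is then one whom Section 5.6 requires to be discontinued.

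**3. Doses between the first progression scan and the confirmation scan.** Dosing is every 21 days. Doses are counted if they fall after the first scan and before the confirmation scan, over every possible position of the scan in the cycle.

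| Interval | Days / 21 | Doses in the gap |
|---|---|---|
| 4 weeks | 28 / 21 = 1.33 | 1 to 2 |
| 6 weeks | 42 / 21 = 2.00 | 2 (1 if a dose is due on the confirmation day and not counted) |
| 8 weeks | 56 / 21 = 2.67 | 2 to 3 |

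Example, assuming the 8-weekly scans are counted from Day 0 and progression is first seen on Day 56. Doses fall on Days 17, 38, 59, 80 and 101. Stopping at the first scan gives 2 doses; stopping at an 8-week confirmation on Day 112 gives 5. If treatment goes on after confirmation, the only fixed limit is 35 cycles, with the last dose on Day 17 + 34 × 21 = 731.

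**4. Is a confirmation scan scheduled if treatment stops at the first progression scan?** Section 7.1.5.1.2 gives post-treatment imaging only to subjects who stop for reasons other than progression. One scheduled scan remains, 30 days after the last dose (Section 7.1.2.7). If the last dose was d days before the progression scan, with d from 0 to 21, that scan falls 30 − d days after it, that is 9 to 30 days. It reaches 28 days only if d ≤ 2. With the general 5-day window it falls at most 35 days after, short of both 42 and 56.

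**The case against.** The best defence is that Section 7.1.2.7 is permissive. An investigator who always stops at confirmed progression breaches neither section. That is true, but the sentence in Section 7.1.2.7 then has no effect, and an investigator who relies on it breaches Section 5.6 in nearly every case (step 2).

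It can also be said that the statistical damage is limited, and this stands. The primary objective uses RECIST 1.1, whose progression rule for target and new lesions needs no confirmation scan. Modified irRC is only to be documented as well, and Section 8.1 specifies no analysis of it.

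A reader might infer more than the documents support:

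- **That there are three incompatible stopping rules.** The duration wording in Sections 1.0, 5.2 and 6.1 can be read as shorthand for the detailed list in Section 5.6. No text says so, which is why it needs aligning, but the firm contradiction is between two sections.
- **That CT stops while treatment continues.** Section 7.1.5.1.3 stands under the heading for post-treatment visits, and Section 7.1.2.7 keeps 8-weekly CT until protocol treatment is completed. The real mismatch in follow-up is documented against confirmed progression.
- **That a late immune response cannot be seen under a stopping rule.** Section 5.6 acts only on confirmed progression. Growth that regresses at the next scan is not confirmed, so treatment and CT go on and the response is recorded. Even after a stop at first progression, the 30-day scan remains and others may be done when clinically indicated.
- **That about 12 of 28 TNBC patients would meet the conflict.** The 12 with progressive disease among 27 evaluable patients in Section 4.2.1 form a response category in a study of pembrolizumab alone. They are not a count of patients who reach a progression rule over up to 24 months, and no matching NSCLC figure is given.

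**Conclusion.** The concern holds for Sections 5.6 and 7.1.2.7 as they now read. A mandatory discontinuation criterion and a statement that confirmed irPD need not end treatment apply to almost the same patients. The only exception is a rise under 5 mm with no new lesion, which needs a nadir sum below 25 mm. The differences in duration, follow-up, prohibited therapies and confirmation interval make the intended rule harder to recover.

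The size is about 1 to 3 doses per affected patient over a confirmation interval of 4 to 8 weeks, assuming dosing on schedule, and more if treatment continues after confirmation. The documents do not allow the number of affected patients to be estimated. The consequences are for post-progression exposure, safety data and modified irRC results. The RECIST 1.1 primary ORR is largely unaffected, so this should not be read as a threat to the primary analysis. How PFS events are dated is a separate matter that this point does not settle.

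**What to change.** Reconcile Sections 1.0, 5.2 (Table 2 footnote), 5.3.2, 5.6, 6.1 (note l), 7.1.2.7, 7.1.5.1.3 and Appendix 12.3 into one rule that:

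1. names the criterion that governs treatment, RECIST 1.1 or modified irRC;
2. says whether progression must be confirmed and, if so, at what single interval;
3. ties entry to telephone-only survival follow-up to that same event, so that any confirmation scan the rule requires is actually scheduled.

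This review takes no position on which stopping rule is right.

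The cost is protocol wording and, depending on the rule chosen, possibly an additional scan on the existing schedule for some patients.

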5.7 Clinical Criteria for Early Trial Termination

Early trial termination will be the result of the criteria specified below:

1. Quality or quantity of data recording is inaccurate or incomplete
2. Poor adherence to protocol and regulatory requirements
3. Incidence or severity of adverse drug reaction in this or other studies indicates a potential health hazard to subjects
4. Plans to modify or discontinue the development of the study drug

In the event of Merck decision to no longer supply study drug, ample notification will be provided so that appropriate adjustments to subject treatment can be made.

6.0 TRIAL FLOW CHART

6.1 Trial Flow Chart

Visit	Screening ^a	Baseline ^b	V1	V2	V3	V4	V5	V6	V7	V8	V9	V10*	EOT	
Day	-28 to -1	-7 to -1	0±5	2±5	4±5	7±5	9±5	11±5	17±5	38±5	59±5	80*±5		
Informed Consent	X													
Inclusion/ Exclusion	X													
Demographics	X													
Medical History	X													
Physical Exam ^c	X		X						X	X	X	X	X	
Height	X													
Weight	X		X						X	X	X	X	X	
ECOG Performance Status	X		X						X	X	X	X	X	
12-Lead ECG and MUGA Scan or Echocardiogram ^d	X												X	
Concomitant Therapies	Continuous from screening period													
Hematology ^e	X		X						X	X	X	X	X	
Clinical Chemistry ^e	X		X						X	X	X	X	X	
Urinalysis ^f	X													
Serum Pregnancy (β-hCG) ^g	X													
Tumor Assessments (modified irRC and RECIST 1:1) ^h	X												X	
Brain MRI (NSCLC patients only) ⁱ	X													
Biopsy ^j			X						X					
Correlative Studies Blood Collection ^k	X								X		X			
AEs and SAEs	From informed consent signing up to 30 days after the last treatment dose^m													
ADV/HSV-tk Administration ^l			X											
Valacyclovir Administration ^l			X											
SBRT Administration ^l				X	X	X	X	X						
Pembrolizumab Administration ^l									X	X	X	X		

Abbreviations: AE = adverse event; ALT = alanine transaminase; ANC = absolute neutrophil count; aPTT = activated partial thromboplastin time; AST = aspartate transaminase; β -hCG, beta-human chorionic gonadotropin; BUN = blood urea nitrogen; CBC = complete blood count; CT = computed tomography; ECG = electrocardiogram; ECOG = Eastern Cooperative Oncology Group; EOT = end of treatment; GM-CSF = granulocyte macrophage colony-stimulating factor; IFN = interferon; IL = interleukin; INR = international normalized ratio; LDH = lactate dehydrogenase; MRI = magnetic resonance imaging; MUGA = multigated acquisition; Q3W = every 3 weeks; PD-1 = programmed death-1; PD-L1 = programmed death-ligand 1; PET = positron emission tomography; p.o. = orally; PT = prothrombin; RT = radiation therapy; SAE = serious adverse event; T3 = triiodothyronine; T4 = thyroxine; Th1 = T-helper; t.i.d. = three times daily; TIL = tumor-infiltrating lymphocyte; TNF = tumor necrosis factor; TSH = thyroid-stimulating hormone; vp = viral particles; WBC = white blood cell. A window of ± 5 days is allowed for visits and study assessments (except as otherwise specified).

a. Within 28 days prior to Day 0 of ADV/HSV-tk.

b. Within 7 days prior to Day 0 of ADV/HSV-tk. Only screening procedures not performed within 7 days of ADV/HSV-tk dosing are required at baseline.

c. The baseline symptom-medical history and physical examination are not required if the screening medical history and physical examination were conducted within 7 to 28 days prior to Day 0 of ADV/HSV-tk. Vital sign (blood pressure, respiratory rate, pulse, and oral temperature) measurements will be performed at each physical exam.

d. A 12-lead ECG will be performed at screening, at EOT, and when clinically indicated. MUGA scan or echocardiogram will be performed only if clinically indicated.

e. A blood sample for CBC with platelet count and differential WBC count will be obtained at screening, on Days 0 and 17, every 3 weeks thereafter until completion of the protocol-specified treatment, at EOT, and when clinically indicated.

If a patient is found to have an ANC $< 1.5 \times 10^9/L$, platelet count $< 100 \times 10^9/L$, or both, the CBC with differential should be repeated at least every other day until the ANC and platelet count have exceeded these values.

A blood sample for clinical chemistry panel (albumin, glucose, sodium, potassium, carbon dioxide, chloride, calcium, BUN, creatinine, total bilirubin, total protein, alkaline phosphatase, AST, and ALT) and evaluation of phosphorus, magnesium, and LDH will be obtained at screening, on Days 0 and 17, every 3 weeks thereafter until completion of the protocol-specified treatment, at EOT, and when clinically indicated. PT/INR and aPTT will be tested at screening and on Day 17. TSH, free T4, and total T3 will be tested at screening and when clinically indicated.

f. Urinalysis (blood, glucose, protein, specific gravity) will be performed at screening and when clinically indicated.

g. For women of childbearing potential, the results of a serum β -hCG pregnancy test must be negative within 7 days before the first treatment dose is administered. If the screening serum β -hCG pregnancy test is performed more than 7 days before ADV/HSV-tk dosing, it must be repeated at baseline, with results known to be negative prior to the first dose of the study treatment. Testing is to be repeated as clinically indicated.

h. For tumor assessments, CT scan of the chest, abdomen, and pelvis will be performed at screening, every 8 weeks thereafter and/or at the discretion of the treating physician, when clinically indicated, and 30 days after the last dose of pembrolizumab. For patients with equivocal CT scan results, PET scan will be performed. For abscopal effect evaluation, CT-based response assessment of non-target lesions will be performed at screening, every 8 weeks thereafter, and 30 days after the last dose of pembrolizumab.

i. Brain MRI will be performed on NSCLC patients only at screening.

j. In patients with accessible tumor, biopsies will be conducted at Day 0 and 3 (± 2) days after the first dose of pembrolizumab. Patients whose disease progresses while on treatment will also undergo biopsy before they start their new treatment. Banked tumor tissue obtained as part of the patient's standard care and additional biopsy tissues will be evaluated for correlative biomarkers including cytokine expression (IL-1, IL-2, IL-6, IL-12, IFN-c, TNF- α , and GM-CSF), TILs, PD-1 and PD-L1 expression, and mutation load. Cytokine expression, TILs, and PD-1 and PD-L1 expression will also be analyzed for abscopal effect evaluation.

k. Blood samples for correlative studies will be collected at screening, 3 (± 2) days after the first dose of pembrolizumab, and end of Cycle 2 of pembrolizumab. An additional sample will be collected from patients whose disease progresses while on treatment. Blood will be collected into standard vacutainer tubes (3 green top tubes).

l. ADV/HSV-tk (5×10^{11} vp) in a 2-mL total volume will be injected intratumorally (single-site injection) on Day 0 of the study. The study coordinator will dispense the 14-day quantity of valacyclovir to the patient on Day 0. The patient will be instructed to take valacyclovir (2 g) p.o. t.i.d. for 14 days (from Day 1 to Day 15 of the study). Primary lung tumors and metastatic lesions (breast and lung) will be treated with SBRT of 30 Gy (6 Gy X 5 fractions). Primary breast

tumors will be treated with a short course (5-8 fractions) of three-dimensional RT. SBRT and three-dimensional RT will be administered over 2 weeks from Day 2 to Day 16 of the study. Pembrolizumab at a dose of 200 mg will be intravenously infused over 30 min Q3W (\pm 1 day) starting on Day 17 (\pm 1 day) of the study and continuing until disease progression, unacceptable toxicity, or up to 24 months (35 cycles) in subjects without disease progression. All subjects who stop pembrolizumab treatment with complete response may be eligible for up to an additional 12 months (17 cycles) of pembrolizumab treatment if they progress after stopping pembrolizumab from the initial treatment phase. The subject must meet the conditions outlined in Section 5.2.3.

m. AEs and SAEs will be captured from the time of informed consent signing up to 30 days after the final dose of pembrolizumab. Study treatment-related SAEs and any study patient death occurring beyond 30 days after the last dose of pembrolizumab should also be reported.

*Patients will be treated until disease progression, unacceptable toxicity, or up to 24 months in subjects without disease progression.

